The screening period will last for up to 28 days. Screening period begins after establishing the subject's initial eligibility and the subject's signing of the ICF. Specimens from tumor tissue must be provided (see Section 3.3.1 for details). The screening period either ends with confirmation of full eligibility and treatment assignment of the subject or with the confirmation that the subject is a screen failure. For information on re-screening, see Section 4.4. For details on re-enrollment, see Section 3.3.1.

Treatment Period:

Each treatment cycle consists of an IV infusion of BMS-986183 monotherapy (BMS-986183 dose escalation [Part 1] and BMS-986183 dose expansion [Part 2]) or BMS-986183 and nivolumab (BMS-986183 and nivolumab dose escalation [Part 3] and BMS-986183 and nivolumab dose expansion [Part 4]) once every 21 days. BMS-986183 monotherapy or BMS-986183 and nivolumab combination therapy will be given on Day 1 of each treatment cycle. The study drug is administered for approximately 1 year (17 cycles, with 21 days/cycle) or until complete remission, progression, unacceptable toxicity, withdrawal of consent, or study closure, whichever occurs first. Study assessments are to be collected as outlined in Table 5.1-1 and Table 5.1-2. Specific requirements for subjects treated with BMS-986183, including dose modifications, dose delays, and treatment discontinuation criteria are described in Section 4.5.2, Section 4.5.4, and Section 3.5, respectively. The treatment period ends when the subject is discontinued from study drug (see Section 3.5). Subjects will then enter the safety follow-up period.

Subjects with a response of SD, PR, or complete response (CR) at the end of a given cycle will continue to the next treatment cycle. Subjects with a confirmed CR at the end of the next cycle will discontinue treatment. Subjects will generally be allowed to continue study therapy for approximately 1 year (17 cycles, with 21 days/cycle) or until the subject meets criteria for discontinuation of study therapy as outlined in Section 3.5, whichever comes first.

Individual subjects with SD or PR may have 6 months (9 cycles, with 21 days/cycle) of extended treatment with BMS-986183 after the first treatment period (17 cycles, with 21 days/cycle) on a case-by-case basis after specific consultation and agreement between the investigator and BMS medical monitor.

Follow-up Period:

Safety Follow-up Period

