All Grade 3 or 4 infusion reactions should be reported within 24 hours to the BMS Medical Monitor and reported as an SAE if criteria are met. Additional samples for PK and immunogenicity assessments, referred to as "Grade 3+ Infusion Reaction Event" samples, will be drawn in cases of Grade 3 to 4 infusion or hypersensitivity reactions (see Section 5.5.1).

If a subject discontinues treatment for an AE, both study drugs should be stopped. If there is an infusion reaction with only 1 study drug and it resolves quickly and is low grade, then the subject can continue both study drugs.

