4.3.2 Nivolumab

Subjects should receive nivolumab at a dose of 360 mg as a 30-minute infusion on Day 1 of each treatment cycle until progression, unacceptable toxicity, withdrawal of consent, or the study ends, whichever occurs first.

For combination treatment in BMS-986183 and nivolumab dose escalation (Part 3) and BMS-986183 and nivolumab dose expansion (Part 4), BMS-986183 will be administered as an infusion for up to 60 minutes. The infusion line containing BMS-986183 should be flushed with an appropriate amount of diluent to ensure that the entire dose is administered and that the infusion line is cleared of any remaining BMS-986183. The nivolumab dose would then be infused not less than 30 minutes from the completion of the BMS-986183 infusion, which would then be infused over a period of 30 minutes.

There will be no individual subject dose escalations or reductions of nivolumab allowed. Subjects may be dosed no less than 18 days from the previous dose during Q3W cycles. For Q3W dosing cycles, subjects may be dosed within $a \pm 3$ -day window. Premedications are not recommended for the first dose of nivolumab.

Subjects should be carefully monitored for infusion reactions during nivolumab administration. If an infusion reaction is noted, subjects should be managed according to Section 4.5.2.2.

Doses of nivolumab may be interrupted, delayed, or discontinued depending on how well the subject tolerates the treatment.

Nivolumab Injection, 100 mg/10 mL (10 mg/mL) is to be administered as an IV infusion through a 0.2- to 1.2-micron pore size, low-protein binding in-line filter at the protocol-specified doses. It is not to be administered as an IV push or bolus injection. Nivolumab Injection can be infused undiluted (10 mg/mL) or diluted with 0.9% Sodium Chloride Injection, USP or 5% Dextrose Injection, USP to protein concentrations as low as 1 mg/mL. Instructions for dilution and infusion of Nivolumab Injection may be provided in the pharmacy manual. Care must be taken to assure sterility of the prepared solution because the product does not contain any antimicrobial preservative or bacteriostatic agent.

Nivolumab infusions are compatible with polyvinyl chloride (or polyolefin containers and infusion sets) and glass bottles.

Separate infusion bags and filters should be used when administering nivolumab and BMS-986183 on the same day.

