5.3 Safety Assessments

All subjects who receive at least 1 dose of BMS-986183 will be evaluated for safety parameters. Additionally, any occurrence of an SAE will be documented and any occurrence of nonserious AEs will be collected as described in Table 5.1-1.

AEs will be coded using the most current version of the Medical Dictionary for Regulatory Activities and reviewed for potential significance and importance. AEs will be evaluated according to the NCI CTCAE v4.03. Subjects should be followed until all AEs for which no clear alternative cause is identified other than to study drug have recovered to baseline or are deemed irreversible by the investigator. Safety assessments will be based on medical review of AE reports and the results of vital sign measurements, PEs (full and targeted), cardiac troponins, ECGs, ECHO/MUGA scans, LFTs, CBCs, and other clinical laboratory tests. In the event of Grade 3 or higher infusion or hypersensitivity reactions, samples for PK and anti-drug antibody (ADA) will be collected. The incidence of AEs will be tabulated and reviewed for potential significance and clinical importance. The schedule of required visits, tests, procedures, and assessments are described in Table 5.1-1 and Table 5.1-2. In limited instances, scheduled events (including events other than safety assessments) can occur outside of the indicated timeframes but the sponsor should be notified.

Some of the assessments referred to in this section may not be captured as data in the eCRF. They are intended to be used as safety monitoring by the treating physician. Additional testing or
assessments may be performed as clinically necessary or where required by institutional or local regulations. If a subject has a delay in study drug administration for any reason, then assessments and laboratory tests (with the exception of any tests needed to ensure subject safety) should be correspondingly delayed with the exception of tumor assessments (ie, continue scans Q6W \pm 1 week regardless of dosing delays).

At baseline, a medical history will be obtained to capture relevant underlying conditions. Baseline signs and symptoms are those that are assessed within 2 weeks prior to subject enrollment. Any new or worsening clinically significant changes must be reported on the appropriate nonserious AE or SAE page.

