- The second secondary objective (to characterize the PK of the total antibody [unconjugated antibody + antibody conjugated to tubulysin or antibody conjugated to any tubulysin metabolites], active ADC [antibody conjugated to tubulysin], and unconjugated tubulysin) of BMS-986183 as monotherapy and in combination with nivolumab will be measured by the following secondary endpoints, when applicable (see Section 5.5 for details):
- Cmax
- Tmax
- AUC(0-T)
- AUC(TAU)
- Ctau

- Ctrough
- CLT
- Vss
- Vz
- AI_Cmax
- AI_Ctau
- AI_AUC(TAU)
- Css,avg
- T-HALF

The third secondary objective (To assess the effect of dosage regimen and exposure [active ADC and unconjugated tubulysin] of BMS-986183 as monotherapy on the QT interval) will be measured by the following secondary endpoints:

• Changes in QTcF (Δ QTcF) from baseline, at selected times

The fourth secondary objective (to characterize the immunogenicity of BMS-986183 as monotherapy and in combination with nivolumab) will be measured by the following secondary endpoints:

• The endpoints of immunogenicity of BMS-986183 as monotherapy and in combination with nivolumab include frequency of different subject immunogenicity status, eg, subject positive ADA, persistent positive ADA and others. Definitions of all the immunogenicity endpoints will be provided in the SAP.

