All subjects will complete up to 4 study periods: screening (up to 28 days), treatment (for approximately 1 year or 17 cycles, with 21 days/cycle), safety follow-up (for a total of 60 days after the last dose of study drug for BMS-986183 dose escalation (Part 1) and BMS 986183 dose expansion (Part 2) and for a total of 100 days after the last dose of study drug for BMS 986183 and nivolumab dose escalation (Part 3) and BMS 986183 and nivolumab dose expansion (Part 4)), with simultaneous response and survival follow-up periods. All subjects will continue to be followed up to 6 months from last dose of study drug. Subjects in BMS 986183 and nivolumab dose escalation (Part 3) and BMS 986183 and nivolumab dose expansion (Part 4) may also be eligible for retreatment with their originally assigned dose regimen with disease progression during follow-up. Only subjects in BMS-986183 dose expansion (Part 2) who have disease progression may be eligible for a combination therapy extension option (their current BMS-986183 dose + flat dose of nivolumab, provided that this combination dose has been found to be safe from BMS-986183 and nivolumab dose escalation (Part 3)). Subjects treated with BMS-986183 and nivolumab combination therapy may be permitted to continue combination therapy beyond initial RECIST v1.1-defined PD, as assessed by the investigator, as long as they meet the criteria specified in the protocol (Section 4.5.7). See [Figure 2.1- 2](#) for a schematic of study periods

Figure 2.1- 2: Dosing (Every 3 Weeks) and Study Periods

^a DLT Assessment Period is only for BMS-986183 dose escalation (Part 1) and BMS-986183 and nivolumab dose escalation (Part 3).

^b Response follow-up is simultaneous with survival follow-up. Only subjects with SD, PR, or CR will be followed for response at least every 3 to 4 months until progression, death, or initiation of new treatment (whichever occurs first).

C = Cycle 1 D = Day.

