4.2.4 Immunogenicity Endpoints

The immunogenicity of BMS-986183 (as monotherapy and in combination with nivolumab) will be measured by assessment of the presence or absence of specific ADA to BMS-986183. The incidence of positive ADA will be calculated.

Validated ADA test methods enable characterization of samples into ADA-positive vs ADA-negative. To classify the ADA status of a participant using data from an in vitro test method, each sample from a participant is categorized based on the following definitions:

Table 4.2.4- 1: Sample ADA Status

Sample ADA Status	Definition
Baseline ADA-positive sample	ADA is detected in the last sample before initiation of treatment
Baseline ADA-negative sample	ADA is not detected in the last sample before initiation of treatment
ADA-positive sample	1) an ADA detected (positive seroconversion) sample in a participant for whom ADA is not detected at baseline, or (2) an ADA detected sample with ADA titer to be at least 4-fold or greater (\geq) than baseline positive titer
ADA-negative sample	After initiation of treatment, ADA not positive sample relative to baseline

Next, using the sample ADA status, participant ADA status is defined as follows:

Table 4.2.4- 2: Participant ADA Status

ADA Status	Definition
Baseline ADA-positive	A participant with baseline ADA-positive sample
ADA-positive	A participant with at least one ADA positive-sample relative to baseline at any time after initiation of treatment
• Persistent Positive (PP)	ADA-positive sample at 2 or more consecutive timepoints, where the first and last ADA-positive samples are at least 16 ^c weeks apart
• Not PP-Last Sample Positive	Not persistent positive with ADA-positive sample at the last

ADA Status	Definition
	sampling timepoint
• Other Positive	Not persistent positive with ADA- negative sample at the last sampling timepoint
Neutralizing Positive:	At least one ADA-positive sample with neutralizing antibodies detected.
ADA-negative	A participant with no ADA-positive sample after the initiation of treatment

^c 16 week threshold was chosen based on the planned ADA blood sampling every four cycles of study therapy.

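### The 16-week persistent-positive ADA threshold rests on sampling every four cycles, but four 21-day cycles are 12 weeks, so two consecutive on-time positives cannot qualify

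*SAP*

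**What the plan says.** Table 4.2.4-2 in SAP Section 4.2.4 defines the persistent-positive subclass as "ADA-positive sample at 2 or more consecutive timepoints, where the first and last ADA-positive samples are at least" 16 weeks apart. The footnote to that figure reads "16 week threshold was chosen based on the planned ADA blood sampling every four cycles of study therapy".

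The cycle length is the same in both documents and all four Parts. SAP Section 2.1 describes "treatment (for approximately 1 year or 17 cycles, with 21 days/cycle". Protocol Section 3.1 sets infusions once every 21 days and adds that "BMS-986183 monotherapy or BMS-986183 and nivolumab combination therapy will be given on Day 1 of each treatment cycle". The exposure definitions in SAP Table 7.4.1-1 also use a 21-day interval.

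Protocol Section 8.3.2 lists persistent positivity among the secondary immunogenicity statuses and leaves the detail to the SAP: "persistent positive ADA and others. Definitions of all the immunogenicity endpoints will be provided in the SAP". Table 4.2.4-2 is therefore the only definition.

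**The concern.** The footnote ties the threshold to the sampling interval, so 16 weeks should equal four cycles. With a 21-day cycle it does not. The consequence goes beyond wording: if samples are taken every four cycles, a subject positive at two consecutive scheduled samples meets the two-timepoint condition but not the 16-week condition. That subject is reported as *Not PP-Last Sample Positive* or *Other Positive*, depending on the last sample.

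Persistent positivity would then be reported less often than the stated reasoning implies. Whether a two-sample pattern qualifies would also depend on how far dosing had slipped, so two subjects with the same pair of results could be classed differently.

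**Working it through.** **Inputs**
- Threshold: 16 weeks (SAP Table 4.2.4-2).
- Sampling interval: four cycles (footnote to the same table).
- Cycle length: 21 days (SAP Section 2.1; Protocol Section 3.1).
- Visit window: ±3 days. Protocol Section 4.3.2 gives this for nivolumab and also states "Subjects may be dosed no less than 18 days from the previous dose during Q3W cycles". Applying it to the monotherapy Parts is an assumption.

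**1. Can the plan's figure be reproduced?** Interval in weeks = cycles × days per cycle ÷ 7.
- 21-day cycle: 4 × 21 = 84 days; 84 ÷ 7 = 12.0 weeks.
- 28-day cycle: 4 × 28 = 112 days; 112 ÷ 7 = 16.0 weeks.
- In reverse: 112 ÷ 21 = 5.33 cycles, not a whole number.

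The figure is reproduced only with a 28-day cycle. The threshold exceeds its stated basis by 16 − 12 = 4 weeks, and 4 ÷ 12 = 33%.

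**2. Do visit windows close the gap?**

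| Two consecutive samples, four cycles apart | Days | Weeks | Short of 112 days by |
|---|---|---|---|
| Earliest, ±3 days at each sample | 84 − 6 = 78 | 11.1 | 34 |
| Nominal | 84 | 12.0 | 28 |
| Latest, ±3 days at each sample | 84 + 6 = 90 | 12.9 | 22 |
| All four dosing intervals 3 days late | 4 × 24 = 96 | 13.7 | 16 |

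None reaches 112 days.

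**3. What does qualify?** The next span on a four-cycle grid is 8 × 21 = 168 days = 24 weeks, which takes three consecutive positives.

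**4. Illustration over 17 cycles.** Assume the first on-treatment sample is at Cycle 5. Samples at Cycles 5, 9, 13 and 17 fall on days 84, 168, 252 and 336 after the first dose, or weeks 12, 24, 36 and 48. The three adjacent gaps are each 12 weeks: 0 of 3 meet a 16-week rule and 3 of 3 meet a 12-week rule.

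**5. Routes by which two positives could still qualify.**
- Dose delay: Protocol Section 5.3 says that when dosing is delayed, assessments and laboratory tests "should be correspondingly delayed with the exception of tumor assessments". From the nominal schedule, 112 − 84 = 28 days of cumulative delay is needed.
- Extra samples: Protocol Section 3.7 provides PK and immunogenicity samples that "will be drawn in cases of Grade 3 to 4 infusion or hypersensitivity reactions". These are event-driven and do not alter the routine rule.

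**The case against.** The strongest counter-argument is that the actual ADA schedule cannot be seen. The sampling tables belonging to Protocol Section 5.5.1 are not readable in the text available. The footnote may describe only the later part of the schedule, and samples early in treatment, at end of treatment or at follow-up could produce spans of 16 weeks or more without a third positive. This stands as a limit on the practical effect. It does not rescue the footnote: if sampling is denser, the footnote misdescribes the schedule; if it is every four cycles, the threshold does not match it.

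A second argument is that a span between one interval (12 weeks) and two (24 weeks) is a coherent choice, since it demands persistence beyond a single interval. That is true of the rule in isolation, but it is not the reason the SAP gives, and on the footnote's schedule it makes the two-timepoint wording inoperative for on-time samples.

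Third, delays are foreseen in the protocol and 28 days could accumulate over four cycles, so 13.7 weeks is a ceiling only when dosing stays within its window. This is also correct, but such pairs are no longer on-time samples.

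Finally, the endpoint is descriptive, the trial tests no formal hypothesis, and overall ADA incidence is untouched. That holds the point at something that should be corrected, not something that threatens the trial's conclusions.

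**Conclusion.** The concern holds. The 16-week threshold cannot follow from sampling every four 21-day cycles; that basis gives 12 weeks, 4 weeks less. On the footnote's schedule no pair of consecutive on-time positives qualifies, and three are needed.

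The mismatch between threshold, footnote and cycle length is certain. Its effect on classification depends on the footnote describing the real schedule, on dosing running close to time, and on the nivolumab window applying in all Parts. The documents do not show whether the threshold or its rationale is the error, and the number of subjects affected cannot be estimated. Overall ADA incidence, sample size and error rates are unaffected; what may change is who is reported as persistent positive.

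**What to change.** Check the threshold against the actual ADA sampling table before analysis, then take one of two routes.

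- **If sampling is every four cycles:** set the threshold in Table 4.2.4-2 and its footnote to one interval less a visit-window allowance. At least 11 weeks (77 days) would capture the 78-day earliest pair. If the team also wants to cover four consecutive minimum intervals of 18 days (4 × 18 = 72 days, 10.3 weeks), the allowance must be wider.
- **If 16 weeks is kept as a fixed standard:** delete the four-cycle rationale, give the real one, and also report persistent positivity under the one-interval (12-week) definition.

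If sampling proves denser than every four cycles, correct the footnote to describe it and justify the threshold from that schedule. The cost is SAP wording and one derivation parameter; no visit, sample or treatment procedure changes.

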4.3.4 ADME-related genes

DNA variants in ADME-related genes from the Core and Extended ADME gene lists may be determined.

5 SAMPLE SIZE AND POWER

Dose Escalation (Parts 1 and 3): A total of approximately 30 evaluable subjects are expected to be treated during BMS-986183 dose escalation (Part 1), and approximately 21 evaluable subjects in BMS-986183 and nivolumab dose escalation (Part 3), assuming 4 dose levels (3 to 6 subjects for each dose level) will be evaluated. In BMS-986183 dose escalation (Part 1) of the study, the sample size per dose level cannot be precisely determined but depends on the observed DLT and the decision rules of mTPI. An initial cohort of 1 to 2 subjects will be enrolled sequentially to dose level cohorts 1 to 3 in BMS-986183 dose escalation (Part 1) (as long as no DLTs are observed or criteria for transitioning from 2-fold increment to modified Fibonacci criteria are not met). Once the first DLT is observed or after the first 3 dose level cohorts with no DLT observed, then 3 to 4 subjects will be enrolled in each dose level cohort (including the current cohort). For the first dose level cohorts of BMS-986183 and nivolumab dose escalation (Part 3), 3 to 4 evaluable subjects may be enrolled. Then between 2 and up to 13 DLT evaluable subjects may be enrolled to a given cohort according to mTPI algorithm. Treating additional subjects beyond the 13 would be unlikely to alter the decision specified by the mTPI algorithm.

Dose Expansion (Part 2 and 4): An adaptive design will be used for the expansion cohorts. Approximately 50 subjects in BMS-986183 dose expansion (Part 2) and 50 subjects in BMS-986183 and nivolumab dose expansion (Part 4) with a plasma membrane or cytoplasmic H score of ≥ 50 for GPC-3 expression are expected to be treated in the BMS-986183 monotherapy expansion cohort at the maximally administered dose or the MTD (as determined from BMS-986183 dose escalation (Part 1) and BMS-986183 and nivolumab dose escalation (Part 3)). This number is based on achieving a reasonable precision of the ORR and adequate control on the false negative rate (FNR) and false positive rate (FPR) (assuming a historic and target response rate).

In a BMS-986183 monotherapy expansion cohort or BMS-986183 combination expansion cohort of 50 marker-positive subjects, assuming no adaptation made, if 10 or 13 responses are observed, then the ORR 90% confidence intervals (CIs) are (11%, 32%) and (16%, 38%), respectively. These calculations are based on the Clopper-Pearson method for exact CIs.

In addition, 50 subjects in BMS-986183 dose expansion (Part 2) or BMS-986183 and nivolumab dose expansion (Part 4) provide the following FNR and FPR under assumptions of expected true ORR. For BMS-986183 dose expansion (Part 2), if the true ORR is 20%, then with 50 subjects in the cohort there is 95% and 90% chance of observing at least 5 or 6 responses, respectively, and there is a 5% chance of observing 4 or fewer responses (FNR). For BMS-986183 and nivolumab dose expansion (Part 4), if the true ORR is 30%, then with 50 subjects in the cohort there is a 96% and 92% chance of observing at least 10 or 11 responses, respectively, and there is a 4% chance of observing 9 or fewer responses (FNR).

Adaptive Design: BMS-986183 dose expansion (Part 2) and BMS-986183 and nivolumab dose expansion (Part 4) will begin enrolling subjects with plasma membrane or cytoplasmic H score ≥ 50 . Decisions to change the H-score cutoff for BMS-986183 dose expansion (Part 2) will not be made until the following occur:

- 1) Approximately 10 response-evaluable subjects are available with mH-score ≥ 150 , or
- 2) Approximately 10 response-evaluable subjects are available with mH-score < 50 and cytoplasmic H score ≥ 50 .

Under 1) if 0 responses are observed with mH-score ≥ 150 (and no other responses in the study population for the expansion cohort are observed), then the expansion cohort may stop for futility. More generally, the statistical method to guide the determination of insufficient response is Bayesian predictive probability.¹ Under 1), if predictive probability of success is less than a pre-specified futility threshold, where success means a posterior response rate is greater than the target null efficacy rate with a very high probability at the end of study, the expansion cohort may stop for futility. A decision to stop the expansion cohort will be based not only on response but also on the totality of the safety, efficacy, and PK/pharmacodynamic data.

Under 2) if 0 responses are observed with mH-score < 50 and cytoplasmic H-score ≥ 50 , then the study population may be restricted to mH-score ≥ 50 . More generally, if predictive probability of success is less than a pre-specified futility threshold, where success means a posterior response rate is greater than the target null efficacy rate with a very high probability at the end of study, the expansion cohort may be restricted to mH-score ≥ 50 .

Enrollment will continue while interim analyses are conducted. For the remainder of the dose expansion, assuming the study is not stopped for futility, ongoing assessment of the responses may result in 3 additional adaptations, depending on whether 1) or 2) is achieved first. If 1) occurs first, then when 2) occurs, if predictive probability is less than a pre-specified futility threshold, the study population may be restricted to mH-score ≥ 50 . If 2) occurs first, then when 1) occurs, if predictive probability is less than the pre-specified futility threshold, the study may be stopped for futility.

The third possible adaptation may be considered once the population is restricted to mH-score ≥ 50 . Depending on the number of responses in the mH-score < 150 (i.e., if 0 responses) enrollment may be further restricted to subjects with mH-score ≥ 150 . Once the biomarker threshold is identified, the cohort may be expanded to ensure adequate subjects from the finalized population of interest for achieving a reasonable precision of ORR.

Simulations were conducted to understand the operational characteristics of the design under a variety of scenarios. For example, assuming a target null efficacy rate of 5%, in the scenario where response rates in all subpopulations were no better than 5%, the observed false positive rate was 8.6% using a 1-sided test, indicating control of Type 1 error. In addition, the average sample size across simulations was 36 subjects. In the scenario where response rate in the mH-score ≥ 50 was 20% and response rate in the mH-score < 50 and cytoplasmic H-score ≥ 50 is 5%, the observed power was 80.6%. In short, the design has adequate power to detect a variety of alternative scenarios with response rates $\geq 20\%$ in subpopulations while maintaining adequate control of Type 1 error with expected sample sizes < 50 .

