Enrollment will continue while interim analyses are conducted. For the remainder of the dose expansion, assuming the study is not stopped for futility, ongoing assessment of the responses may result in 3 additional adaptations, depending on whether 1) or 2) is achieved first. If 1) occurs first, then when 2) occurs, if predictive probability is less than a pre-specified futility threshold, the study population may be restricted to mH-score \geq 50. If 2) occurs first, then when 1) occurs, if predictive probability is less than the pre-specified futility threshold, the study may be stopped for futility.

The third possible adaptation may be considered once the population is restricted to mH-score \geq 50. Depending on the number of responses in the mH-score < 150 (ie, if 0 responses) enrollment may be further restricted to subjects with mH-score \geq 150.

Simulations were conducted to understand the operational characteristics of the design under a variety of scenarios, and the design has adequate power to detect a variety of alternative scenarios with response rates $\geq 20\%$ in subpopulations while maintaining adequate control of Type 1 error with expected sample sizes < 50.

Endpoints: Primary endpoints are incidence of AEs at its worst grade, serious AEs at its worst grade, AEs leading to discontinuations, deaths, and frequency of laboratory test toxicity grade shifting from baseline. Secondary endpoints are best overall response (BOR), ORR, duration of response (DoR), PFS, PFS at week 't', PK measures, changes in Fridericia-corrected QT interval (Δ QTcF), and frequency of different subject immunogenicity status (eg, subject positive antidrug antibodies, persistent positive antidrug antibodies, and others). Exploratory endpoints will also be assessed.

Analyses: Only the safety analysis and efficacy endpoint analysis are described below. Please refer to Section 8 of the protocol for a complete description of statistical analyses.

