In a BMS-986183 monotherapy expansion cohort or BMS-986183 combination expansion cohort of 50 marker-positive subjects, assuming no adaptation made, if 10 or 13 responses are observed, then the ORR 90% confidence intervals (CIs) are (11%, 32%) and (16%, 38%), respectively. These calculations are based on the Clopper-Pearson method for exact CIs.

In addition, 50 subjects in BMS-986183 dose expansion (Part 2) or BMS-986183 and nivolumab dose expansion (Part 4) provide the following FNR and FPR under assumptions of expected true ORR. For BMS-986183 dose expansion (Part 2), if the true ORR is 20%, then with 50 subjects in the cohort there is 98% and 95% chance of observing at least 5 or 6 responses, respectively, and there is a 2% chance of observing 4 or fewer responses (FNR). If the true ORR is only 5%, then there is 10% and 4% chance respectively of observing at least 5 and at least 6 responses among 50 subjects (FPR). For BMS-986183 and nivolumab dose expansion (Part 4), if the true ORR is 30%, then with 50 subjects in the cohort there is a 96% and 92% chance of observing at least 10 or 11 responses, respectively, and there is a 4% chance of observing 9 or fewer responses (FNR). If the true ORR is only 15%, then there is 21% and 12% chance respectively of observing at least 10 and at least 11 responses among 50 subjects (FPR).

For more details on the H score cutoff, see Section 5.6.1.

Adaptive Design: BMS-986183 dose expansion (Part 2) and BMS-986183 and nivolumab dose expansion (Part 4) will begin enrolling subjects with plasma membrane or cytoplasmic H score \geq 50. Decisions to change the H-score cutoff for BMS-986183 dose expansion (Part 2) will not be made until the following occur:

- 1) Approximately 10 response-evaluable subjects are available with mH-score \geq 150, or
- 2) Approximately 10 response-evaluable subjects are available with mH-score < 50 and cytoplasmic H score ≥ 50 .

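### SAP section 5 and the protocol synopsis misstate the Part 2 response probabilities at n = 50 and ORR 20%, contradict protocol 8.1.2, and announce a false positive rate that they do not give

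*SAP*

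**What the plan says.** Three places give operating characteristics for a Part 2 cohort of 50 subjects with a true ORR of 20%.

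- **SAP section 5** and the **protocol synopsis** (Statistical Considerations) use the same words: "there is 95% and 90% chance of observing at least 5 or 6 responses, respectively, and there is a 5% chance" of 4 or fewer responses, labelled the FNR.
- **Protocol 8.1.2** has, for the same cohort size, ORR and counts: "there is 98% and 95% chance of observing at least 5 or 6 responses, respectively, and there is a 2% chance" of 4 or fewer.

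The SAP and the synopsis introduce their figures by saying that the 50 subjects "provide the following FNR and FPR under assumptions of expected true ORR". Only FNR figures follow. Protocol 8.1.2 has the same introduction and does supply the FPRs. For Part 2: "If the true ORR is only 5%, then there is 10% and 4% chance respectively of observing at least 5 and at least 6" responses. For Part 4: "If the true ORR is only 15%, then there is 21% and 12% chance respectively of observing at least 10 and at least 11" responses.

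Elsewhere in SAP section 5 the only false positive rate comes from simulating the adaptive design with a 5% null rate: "the observed false positive rate was 8.6% using a 1-sided test, indicating control of Type 1 error". The synopsis gives no number. It says only that the design has adequate power "while maintaining adequate control of Type 1 error with expected sample sizes < 50".

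**The concern.** Two sets of probabilities for identical events under identical assumptions cannot both be right. SAP section 5 says that the choice of 50 subjects rests on the precision of the ORR estimate and on acceptable FNR and FPR. If the Part 2 FNR printed there is wrong and the matching FPR is absent, a reader of the SAP or synopsis cannot set the two fixed-sample error rates against each other. The gap is widest for Part 4, where the SAP shows an FNR of 4% but not the FPRs of 21% and 12% that go with the same response counts. A reader comparing the documents also cannot tell which Part 2 figures are intended.

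**Working it through.** **Inputs.** n = 50 and true ORR 20%, with counts of at least 5, at least 6, and 4 or fewer (SAP section 5, synopsis and protocol 8.1.2). For the FPRs, ORR 5% with counts 5 and 6 (Part 2) and ORR 15% with counts 10 and 11 (Part 4), from protocol 8.1.2. For a method check, Part 4 at ORR 30% (SAP section 5).

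**Formula.** With X ~ Binomial(n, p), P(X ≤ c) = Σ C(n,k) p^k (1−p)^(n−k) for k = 0 to c, and P(X ≥ r) = 1 − P(X ≤ r−1).

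**Part 2, n = 50, p = 0.20.** The terms for k = 0 to 4 are 0.0014%, 0.0178%, 0.1093%, 0.4371% and 1.2840%, which sum to 1.85%. The term for k = 5 is 2.95%, so P(X ≤ 5) = 4.80%. The term for k = 6 is 5.54%, so P(X ≥ 7) = 100 − 4.80 − 5.54 = 89.66%.

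| Event | SAP 5 and synopsis | Protocol 8.1.2 | Exact |
|---|---|---|---|
| 5 or more | 95% | 98% | 98.15% |
| 6 or more | 90% | 95% | 95.20% |
| 4 or fewer (FNR) | 5% | 2% | 1.85% |

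The SAP and synopsis figures miss by 3.2, 5.2 and 3.2 percentage points. The FNR ratio is 5 / 1.85 = 2.7. The 8.1.2 figures reproduce.

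**Method check, Part 4, p = 0.30.** P(X ≥ 10) = 95.98%, P(X ≥ 11) = 92.11% and P(X ≤ 9) = 4.02%, against 96%, 92% and 4% in the SAP. These agree, so the error is confined to the Part 2 figures.

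**Could another reading produce 95/90/5?**

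- *Approximations at n = 50, p = 0.20.* The normal approximation gives 96.1% and 92.1% without continuity correction, and 97.4% and 94.4% with it. The Poisson gives 97.1% and 93.3%. None fits.
- *Another sample size at 20%.* No n from 36 to 55 rounds to 95/90/5. The nearest are n = 43 (95/89/5) and n = 44 (96/90/4). P(X ≥ 5) rises with n and is already 87.3% at n = 36 and 99.1% at n = 55, so looking further is pointless.
- *Another ORR at n = 50.* A rate near 17.65% would give 95.5%, 89.7% and 4.5%, but all three places state 20%.
- *Counts one higher at n = 50, p = 0.20.* P(X ≥ 6) = 95.2%, P(X ≥ 7) = 89.7% and P(X ≤ 5) = 4.8%. These round to the printed figures, which suggests an off-by-one slip but does not prove it.

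**Fixed-sample FPRs missing from the SAP and synopsis.**

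| Part | ORR | Count | Exact | Protocol 8.1.2 |
|---|---|---|---|---|
| 2 | 5% | ≥ 5 | 10.4% | 10% |
| 2 | 5% | ≥ 6 | 3.8% | 4% |
| 4 | 15% | ≥ 10 | 20.9% | 21% |
| 4 | 15% | ≥ 11 | 12.0% | 12% |

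All four values in 8.1.2 reproduce.

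**The case against.** The strongest reply is that nothing turns on these numbers. The study has no formal hypothesis test. Counts of 5 and 6 trigger no action: futility and H-score restriction rest on Bayesian predictive probability and the totality of the data. The stated FNR is worse than the true one, so the design is undersold rather than oversold. All of that stands, and it is why the point is minor.

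The second reply is that the missing FPR is only a drafting gap. The SAP does report a simulated FPR of 8.6% at a 5% null, with 80.6% power in one scenario, so a reader can weigh the two error rates for the adaptive Part 2 design. A synopsis may also leave detail to the body of the protocol. This stands in part. The simulated rate is for the adaptive design at a 5% null, so it is not the counterpart of the fixed-sample FNR printed beside it, and it says nothing about Part 4 at 15%. The synopsis has no numeric FPR at all. Both paragraphs still announce a quantity that does not follow.

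A third reply is that the SAP does agree with the protocol, namely with its synopsis. That is true, and it places the contradiction inside the protocol as well as between the documents. None of these replies rescues the printed 95%/90%/5%.

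**Conclusion.** The concern holds, at minor severity. For n = 50 and a true ORR of 20%, the Part 2 figures in SAP section 5 and the synopsis are wrong. Protocol 8.1.2 has them right, and it is the only place with the fixed-sample FPRs that the other two announce. The conclusion assumes only independent binary responses with a common rate and no adaptation, which is the basis on which protocol 8.1.2 and the Part 4 figures reproduce. The sample size, the 90% confidence intervals for 10 and 13 responses (11.3% to 31.6% and 16.1% to 38.1%, as printed after rounding), the Part 4 FNR figures, the simulation results and the planned analyses are unaffected. The off-by-one origin is an inference from the numbers, and the verdict does not depend on it.

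**What to change.** In SAP section 5 and the protocol synopsis:

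1. Replace the Part 2 figures 95%, 90% and 5% with 98%, 95% and 2%.
2. Add the FPRs from protocol 8.1.2 (Part 2 at ORR 5%: 10% and 4%; Part 4 at ORR 15%: 21% and 12%). Label them as fixed-sample values without adaptation, so that they are not confused with the simulated 8.6%. In the synopsis, a cross-reference to 8.1.2 would also close the gap if space is short.

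The cost is a wording correction in two places, with no extra subjects and no new analyses.
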